Treatment-emergent adverse events: Table 1 summarizes adverse events, regardless of relationship, to infigratinib as a single agent at the maximum tolerated dose of 125 mg, 3 weeks on, 1 week off (N = 433 subjects), and Table 2 summarizes Grade 3 to 4 adverse events. The on-target effects on calcium-phosphorus homeostasis result in the observed increases in calcium (13.4% any grade, 3.2% Grade 3-4), phosphorus (61.2% any grade, 6.7% Grade 3 to 4), and creatinine (23.8% any grade). These are not associated with clinical symptoms and in general have been mild to moderate in severity, manageable, and reversible. Guidelines for management of on-target hyperphosphatemia have been implemented.

Ocular adverse events (corneal or retinal) occur in about 50% of subjects, but in general are mild to moderate in severity and reversible: for example, Grade 1 to 2 dry eye was reported in 21.5% and Grade 1 to 2 blurry vision in 9.9%. Grade 3 ocular events occurred in 3% of subjects; no Grade 4 ocular events have been reported. Grade 3 adverse events of cataract (N = 3, 0.7%), visual impairment (N = 2, 0.5%), and keratitis (N = 2, 0.5%) were the events that

occurred in more than one subject; others were reported once. Adverse events of blurred vision, visual impairment, and keratitis led to study drug discontinuation for N = 2, 0.5% subjects each. Since the cornea and retina were identified from preclinical safety studies as a potential target organ of interest, protocol-mandated ophthalmologic examinations have been performed routinely and frequently throughout studies.

Subjects have been monitored for potential QT prolongation: N = 3 (0.7%) of subjects have had a new QTc value > 500 msec, N = 4 (1.0%) have had a QTcF change of > 60 msec, and N = 63 (15.0%) have had a QTcF change > 30 and  $\leq$  60 msec. None of these events was considered serious nor led to treatment withdrawal or dose reduction/interruption. Subjects have also been monitored for potential decrease in ventricular ejection fraction by echocardiogram or multi-gated acquisition. N = 6 (1.4%) of subjects had a Grade 2 abnormality (no Grade 3-4 events), which did not lead to study drug discontinuation.

Other notable adverse events include stomatitis (34.9%) and alopecia (26.8%).

**Table 1:** Adverse events occurring in ≥ 10% of adult oncology subjects treated with infigratinib monotherapy

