#### Management of Hyperphosphatemia

Hyperphosphatemia is a recognized on-target effect of potent and selective inhibitors of the FGFR pathway.

The goal of a low-phosphate diet, when one is recommended per management strategy below, is to restrict dietary phosphate to 600 to 800 mg/day by avoiding high-phosphate foods. High-phosphate foods include dairy products; meats, nuts, and other high-protein foods; processed foods; and dark colas. In general, subjects will be instructed to liberalize their diet on days they are not taking infigratinib (including Days 22 to 28, and during interruption of infigratinib for indications other than hyperphosphatemia), unless their serum phosphorus is currently > 5.5 mg/dL. Similarly, subjects who are taking sevelamer (phosphate-lowering medication) will be instructed to hold it on days they are not taking infigratinib (including Days 22 to 28, and during interruption of infigratinib for indications other than hyperphosphatemia), unless their serum phosphorus is currently > 5.5 mg/dL.

Below is the recommended management strategy for hyperphosphatemia. Section 6 also outlines instructions for when to interrupt and/or dose-reduce infigratinib in addition to these recommendations for management. Notably, these instructions for increased monitoring of serum phosphorus, interruption, and dose reduction begin if serum phosphorus > 7.0 mg/dL.

All subjects will have a serum phosphorus checked on C1D4:

- If serum phosphorus > 5.5 and ≤ 7.0 mg/dL, subjects will be instructed to follow a low-phosphate diet and to take sevelamer 800 mg orally 3 times daily with meals.
- If serum phosphorus > 7.0 mg/dL, subjects will be instructed to follow a low-phosphate diet and to take sevelamer 1200 mg orally 3 times daily with meals.

All subjects will have a serum phosphorus checked on Cycle 1 Day 15:

- For subjects who are not currently following a low-phosphate diet or taking sevelamer:
  - If serum phosphorus > 5.5 and ≤ 7.0 mg/dL, subjects will be instructed to follow a low-phosphate diet and to take sevelamer 800 mg orally 3 times daily with meals.
  - If serum phosphorus > 7.0 mg/dL, subjects will be instructed to follow a low-phosphate diet and to take sevelamer 1200 mg orally 3 times daily with meals.
- For subjects who are currently following a low-phosphate diet and taking sevelamer:
  - o If serum phosphorus < 5.0 mg/dL, subjects will be given the option of liberalizing their diet or stopping the sevelamer (not both).

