### 7. ADVERSE EVENTS AND REPORTING PROCEDURES

### 7.1 Potential Adverse Events

### 7.1.1 Related to Study Drug (Infigratinib)

- Adverse events related to calcium/phosphorous homeostasis are expected and on-target effects of infigratinib. Hyperphosphatemia in particular is a reliable biomarker of pathway inhibition and rapidly normalizes upon drug discontinuation without sequelae. Among 433 subjects treated with infigratinib monotherapy, hyperphosphatemia was seen in 62% and in 7% it was Grade 3 or 4. Adverse events associated with calcium/phosphate imbalance (including soft tissue mineralization or ectopic calcifications) have been rare. There have been 3 suspected unexpected SAEs reported related to calcium/phosphorus homeostasis: (1) hepatic failure due to lesion calcification occurring over 6 months after study drug discontinuation, (2) one episode of hypercalcemia, and (3) one episode of hypophosphatemia/hypocalcemia.
- Ophthalmologic adverse events may occur with infigratinib, and mandated ophthalmologic examinations have been performed routinely and frequently. Most of these events are Grade 1 or 2: for example, dry eye in 22% and blurry vision in 10%. Grade 3 ocular events have occurred in 3%, and no Grade 4 ocular events have occurred. Grade 3 ocular events included cataract (0.7%), visual impairment (0.5%), and keratitis (0.5%).
- Gastrointestinal adverse events are frequently reported. For subjects treated with monotherapy, the most frequent GI AEs (regardless of relationship to study drug) were constipation (37%), decreased appetite (30%), nausea (29%), diarrhea (27%), vomiting (20%), and dyspepsia (15%). Stomatitis was reported in 35%, and in 5% was Grade 3 or 4.

- Skin, hair, and nail changes are frequently reported. For subjects treated with monotherapy, 27% experienced alopecia, 13% experienced dry skin, and 12% experienced palmar-plantar erythrodysaesthesia syndrome.
- For others, please see Section 2.2 (especially Tables 2 to 4) and the Investigator's Brochure.
- 7.1.2 Related to Tamoxifen (Cohort 1) (reported percentages are from N = 3,094 subjects in the ATAC trial)
  - Hot flashes (64%) (placebo 48%)
  - Vaginal discharge (30%) (placebo 15%)
  - Nausea (26%) (placebo 24%)
  - Fluid retention (32%) (placebo 30%)
  - Mood disturbances
  - Thrombotic events (0.8% deep vein thrombosis, 0.5% pulmonary embolism, 0.4% superficial phlebitis)
  - For others, please see tamoxifen package insert from the FDA.

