# 9. STUDY CALENDAR

	Screening	On Treatment (1 Cycle = 28 days)						Post-Treatment			
2	(Within	Cycle 1			Cycle 2		Cycles ≥ 3	End of Treatment /	30-day		
	21 days of Cycle 1, Day 0)	Day 1 (± 3 days)	Day 4 (± 1 day)	Day 15 (± 3 days)	Day 1 (± 3 days)	Day 15 (± 3 days)	Day 1 (± 3 days)	withdrawal (0 to 14 days from decision to discontinue) 	Follow-up Safety Visit (+ 7 days)  F	Other Follow-up 	
Informed Consent 	Х										
Medical/Tumor History 	х										
Physical Examination (within 24 hours prior to start of each cycle) 	x	х		x	х		x	X	x	( X )	
ECOG Performance Status 	х	х		Х	Х		Х	Х	Х	( X )	
Safety Labs/Measurements	5										
Vital Signs (within 24 hours prior to start of each cycle) 	х	х		х	х		х	х	х	( X )	
Hematology (CBC, differential, platelets) 	х	х		х	х	Х	х	х		( X )	
Complete metabolic panel 7	Х	х	Х	Х	Х	Х	X	Х		(X)	
Amylase, lipase 	х	Х		Х	Х	Х	Х	х		( X )	
Calcium, magnesium, phosphorus 	х	х	х	х	х	Х	x	х		( X )	
Urinalysis 10	Х										
Pregnancy Test 11	х	Х						х			
Electrocardiogram 12	х				х		C4D1, C6D1 (± 7 days) then every 6 cycles (all ± 14 days)	х			
Transthoracic echocardiogram	х				х			х			
Ophthalmology evaluation 	х				X ± 7 da ys		C3D1, C4D1, C6D1 (± 7 days), then every 3 cycles (± 14 days)	х			

IRB-53650 Version 11 Page 52 of 72 11 November 2021

Hormone Receptor-positive, HER2-negative, FGFR-altered Advanced Breast Cancer

	Screening			On Tre	eatment (	Post-Treatment				
	(Within	Cycle 1		Сус	ele 2	Cycles ≥ 3	End of Treatment /	30-day		
Protocol Activity	21 days of Cycle 1, Day 0)	Day 1 (± 3 days)	Day 4 (± 1 day)	Day 15 (± 3 days)	Day 1 (± 3 days)	Day 15 (± 3 days)	Day 1 (± 3 days)	withdrawal (0 to 14 days from decision to discontinue) 	Follow-up Safety Visit (+ 7 days)  Fol	
Registration 	≤ 7 days bef Cycle 1, Day 1									
Treatment										
Infigratinib administration 			1 week off			3 weeks on / 1 week off 3 weeks on / 1 week off				
Cohort 1: Tamoxifen administration 			Continuous		Continuous		Continuous			
Tumor Assessment										
CT (chest, abdomen, pelvis) 	х						C3D1 (+7 days), then every 2 cycle (± 7 days)	( X )		
Plasma collection 		х		х				Х		
Research tumor biopsy 19	Х			х						
Tumor sequencing 	Х									

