#### Score Definition

- 0 Fully active, able to carry on all pre-disease activities without restriction
- 1 Restricted in physically strenuous activity but ambulatory and able to carry out work of a light or sedentary nature, eg, light house work or office work
- 2 Ambulatory and capable of all selfcare but unable to carry out any work activities. Up and about more than 50% of waking hours
- 3 Capable of only limited selfcare, confined to bed or chair more than 50% of waking hours
- 4 Completely disabled. Cannot carry on any selfcare. Totally confined to bed or chair
- 5 Dead
- 5. Vital signs: Blood pressure, pulse rate, and body temperature to be recorded in the same position, either supine or sitting.
- **6. Hematology:** No need to repeat on C1D1 if baseline assessment performed within 72 hours prior to that date. On treatment, to be performed prior to dosing with study medications unless otherwise indicated. Lab abnormalities that are adverse events specified in Table 6 must be followed at least weekly until resolution to the grade specified in Table 6.
- 7. Complete metabolic panel: No need to repeat on C1D1 if baseline assessment performed within 72 hours prior to that date. Lab abnormalities that are adverse events specified in Table 6 must be followed at least weekly until resolution to the grade specified in Table 6.
- **8. Amylase**, **lipase**: No need to repeat on C1D1 if baseline assessment performed within 72 hours prior to that date. Lab abnormalities that are adverse events specified in Table 6 must be followed at least weekly until resolution to the grade specified in Table 6.
- **9.** Calcium, magnesium, phosphorus (serum): No need to repeat on C1D1 if baseline assessment performed within 72 hours prior to that date. Lab abnormalities that are adverse events specified in Table 6 must be followed at least weekly until resolution to the grade specified in Table 6.
- **10. Urinalysis:** Macroscopic or microscopic.
- **11. Pregnancy Test:** For female subjects of childbearing potential, a serum or urine pregnancy test must be performed within 7 days of first day of study drug and at end-of-treatment. Additional pregnancy test to be repeated when potential pregnancy is suspected.

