#### 10. MEASUREMENTS

### 10.1 Primary endpoint:

The primary endpoint is the incidence of dose-limiting toxicities (DLTs) in the first 2 cycles of therapy at a specific dose. In Cohort 1, in a subset of subjects who start at infigratinib 100 mg and complete 2 cycles with no DLTs and who remain on study for Cycles 3 and 4, the dose of infigratinib will be increased to 125 mg starting with Cycle 3 and the number of DLTs in Cycles 3 and 4 will be counted toward the primary endpoint (for the 125 mg dose), in addition to the number of DLTs in Cycles 1 and 2 (for the 100 mg dose). For all other subjects, the primary endpoint will be the number of DLTs in Cycles 1 and 2.

DLTs will be graded using NCI CTCAE (Common Terminology Criteria for Adverse Events), v5.0. DLTs will be defined as an adverse event (AE) or abnormal laboratory value at least possibly related to therapy with infigratinib including those AEs and abnormal laboratory values that result in a failure to meet the criteria for re-treatment. The criteria for defining a DLT, which are pre-specified based on the pre-clinical toxicity of infigratinib, are listed in Table 7.

Individual subjects who had a DLT may be retreated, after recovery, at the next lowest dose level.

Investigators will notify QED Therapeutics within 7 days of any DLTs observed.

**Table 7.** Criteria for defining dose-limiting toxicities

TOXICITY	DLT CRITERION
Skipped/ delayed dose	The inability to administer infigratinib on ≥ 75% of scheduled treatment days during cycle 1 at that dose (ie, ≥ 16 days of the 21 days of planned treatment) due to unresolved adverse event of any grade and considered at least possibly, probably, or definitely related to the study drug.
	Delay in 2 nd cycle administration at that dose due to failure of recovery from a possibly, probably, or definitely related adverse event to Grade ≤ 1 or baseline by Day 43 (Day 28 of Cycle 1 + 15 days), except for alopecia.
Blood/ bone marrow	Neutropenia     • Febrile, CTCAE Grade ≥ 3.     • CTCAE Grade ≥ 3 for > 7 consecutive days
	Thrombocytopenia
	Anemia CTCAE Grade 4
Renal/ genitourinary	Creatinine:  • CTCAE Grade 1 for > 7 consecutive days and serum inorganic phosphorus  > 5.5 mg/dL and/or serum total calcium x serum inorganic phosphorus  > 55 mg²/dL² and despite phosphorus lowering therapy for ≥ 14 days
	
 
CTCAE Grade 2 for > 7 consecutive days
 
CTCAE Grade ≥ 3
 

**Table 7.** Criteria for defining dose-limiting toxicities

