TOXICITY	DLT CRITERION	
Hepatic	Bilirubin: • CTCAE Grade 2 for > 7 consecutive days	
	• CTCAE Grade ≥ 3	
	AST or ALT: • Grade 3 for > 7 consecutive days • CTCAE Grade 4	
	Hy's Law	
	
 
ALT or AST ≥ 3 x upper limit of normal (ULN)
 
AND
 
Serum total bilirubin > 2 x ULN
 
	
	For patients with known hepatic metastases:  • AST or ALT > 8 x ULN  OR	
	• AST or ALT > 5 x ULN for ≥ 14 days	
Pancreas	Pancreatitis CTCAE Grade ≥ 2	
	Amylase/lipase (serum-high): CTCAE Grade ≥ 3 asymptomatic amylase and/or asymptomatic lipase not reversible to CTCAE Grade ≤ 2 within 7 days	
Cardiac	QTcF interval > 500ms	
	Other cardiac CTCAE Grade ≥ 3	
Constitutional	Fatigue CTCAE Grade 3 for > 7 consecutive days	
	Fatigue CTCAE Grade 4	
Ocular/visual	Any ocular/visual toxicity CTCAE Grade ≥ 3.	
Gastrointestinal	CTCAE Grade 3 or 4 nausea/vomiting and/or diarrhea despite the use anti-emetic and anti-diarrhea therapy, respectively	
Metabolic/ laboratory	
 
Hyperphosphatemia (serum-high):
 
Serum inorganic phosphorus > 7.0 mg/dL for > 7 consecutive days despite phosphorus-lowering therapy for at least 14 days.
 
Serum inorganic phosphorus > 9.0 mg/dL, despite phosphorus-lowering therapy for at least 14 days.
 
Serum inorganic phosphorus > 10.0 mg/dL
 
Hypercalcemia (serum-high)
 
Serum calcium CTCAE Grade 2 for > 7 consecutive days.
 
Serum calcium CTCAE Grade ≥ 3.
 
	
Other	Any death not clearly due to the underlying disease or known, extraneous causes.	
	Clinical evidence for any grade (CTCAE Grade ≥ 1) of ectopic, de-novo -calcification within the soft tissue including the peri-articular spaces and vascular as well as visceral tissues (eg, kidney, lung, stomach, myocardium, etc.)	
	
 
Any other CTCAE Grade 3 or 4 non-hematological toxicity except with following exclusions:
 
• Alkaline phosphatase CTCAE Grade ≥ 3.
 
• Lymphocytopenia CTCAE Grade ≥ 3 unless considered clinically significant.
 
	

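### Subjects escalated to 125 mg have no Day 15 safety labs in their DLT window (Cycles 3 and 4); the one scheduled value after 125 mg exposure falls nominally 8 days after the last dose

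*Combined protocol and SAP*

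**What the plan says.** Section 10.1 defines the primary endpoint as DLTs in the first two cycles at a given dose. For subjects who finish two cycles at 100 mg without a DLT and stay on study, infigratinib rises to 125 mg at Cycle 3 and "the number of DLTs in Cycles 3 and 4 will be counted toward the primary endpoint (for the 125 mg dose"). Section 12.4 uses these counts. A dose is declared safe on no DLT in 3 subjects or 1 in 6, and the first three at 125 mg can all be escalated subjects.

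In the Section 9 calendar, the row "Calcium, magnesium, phosphorus" and the metabolic panel row are marked at screening, C1D1, C1D4, C1D15, C2D1, C2D15, Day 1 of each cycle from Cycle 3, and End of Treatment. Hematology and amylase/lipase follow the same pattern without C1D4. No footnote adds a draw after a dose increase.

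Extra testing is conditional. The laboratory footnotes state that "Lab abnormalities that are adverse events specified in Table 6 must be followed at least weekly", and in Section 4.1.2 "these instructions for increased monitoring of serum phosphorus, interruption, and dose reduction begin if serum phosphorus > 7.0 mg/dL".

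Many Table 7 DLT criteria need a measured value. Two phosphorus criteria apply only "despite phosphorus-lowering therapy for at least 14 days". The amylase/lipase criterion is "CTCAE Grade ≥ 3 asymptomatic amylase and/or asymptomatic lipase not reversible to CTCAE Grade ≤ 2 within 7 days".

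**The concern.** The DLT window follows the dose level, but the lab schedule follows the study cycle number. The two agree for a subject who starts at a dose. They separate for an escalated subject, whose first two cycles at the highest dose are monitored on the sparse schedule meant for later cycles.

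Day 1 is also a poor time to look. It follows the drug-free Days 22 to 28. Section 7.1.1 says hyperphosphatemia "rapidly normalizes upon drug discontinuation without sequelae". Section 2.2.9 says of the calcium, phosphorus and creatinine rises: "These are not associated with clinical symptoms". Symptoms will therefore not reliably prompt a test. The off week was itself chosen from interruptions for hyperphosphatemia, which began at a median of 22 days and lasted a median of 7.

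At stake is the 125 mg decision. An event that is not measured is not counted, and as few as three subjects with no counted DLT clear the dose. Subject safety is also involved, because the laboratory holds and reductions in Table 6 depend on measured values.

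**Working it through.** The plan gives no figure for this point, so the check is calendar arithmetic.

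**Inputs.** 28-day cycle, 21 days on and 7 off (Section 4; Table 7 confirms 21 planned dosing days). Draw days and visit windows from Section 9: Day 1 ± 3, Day 4 ± 1, Day 15 ± 3. DLT windows from Section 10.1: Cycles 1 and 2 for a subject starting at a dose, Cycles 3 and 4 for one escalated to 125 mg.

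**Time since last dose at a Day 1 draw.** Next Day 1 is Day 29 and the last dose is Day 21: 29 − 21 = 8 days. With ± 3 days this is 5 to 11, if dosing has not yet resumed. A late visit could fall in the first days of the new cycle, up to Day 4, but not near Day 15.

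**Scheduled values in the two-cycle DLT window, after the first dose at that level.**

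| | Starter (Cycles 1–2) | Escalated (Cycles 3–4) |
|---|---|---|
| Metabolic panel; calcium/magnesium/phosphorus | C1D4, C1D15, C2D1, C2D15 = 4 | C4D1 = 1 |
| Hematology; amylase/lipase | C1D15, C2D1, C2D15 = 3 | C4D1 = 1 |
| Day 15 draws, every panel | 2 | 0 |
| Early on-drug draw (C1D4), chemistry and phosphorus only | 1 | 0 |

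C3D1 is not counted because it nominally precedes the first 125 mg dose. Planned dosing days in the escalated window: 2 × 21 = 42.

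**Spacing (nominal study days).** Cycles 1–2, chemistry and phosphorus: 1, 4, 15, 29, 43, then 57; gaps 3, 11, 14, 14, 14. Cycles 3–4: 57, 85, then 113; gaps 28 and 28. The longest gap is 14 days against 28. Draws 28 days apart cannot by themselves establish a criterion that needs more than 7 consecutive days.

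**Phosphorus criteria requiring 14 days of binder.** Binder begun on C1D4 has run 15 − 4 = 11 days by C1D15 nominally, or up to 18 − 3 = 15 with the windows. For a starter these two criteria are therefore tested mainly at C2D15. An escalated subject has no corresponding draw. The criterion above 10.0 mg/dL has no binder condition.

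**Triggers.** Weekly follow-up of Table 6 abnormalities and phosphorus checks every 2 to 3 days above 7.0 mg/dL both need an abnormal value first. The dose increase triggers nothing. A subject with normal values at C3D1 and C4D1 has no protocol-driven test in between.

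**The case against.** Four points against the concern have force.

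- **Reversal time.** Rapid normalization off drug is documented only for hyperphosphatemia. Section 2.2.9 calls the calcium and creatinine changes reversible in general but gives no time. Nothing is given for AST/ALT, bilirubin, amylase/lipase or blood counts, and Table 6 provides for several of these not resolving within 7 or 14 days. Such events could still appear at C4D1 or C5D1. This stands and limits the claim.
- **Existing triggers.** A phosphorus value that needs sevelamer counts as an adverse event under Section 7.2 and so calls for weekly follow-up, even below 7.0 mg/dL. Clinically indicated tests and End of Treatment labs also remain. This narrows the exposed group but does not help a subject whose Day 1 values are normal.
- **Opposite bias.** Section 12.4 notes that intra-subject escalation may blame the dose for toxicity that comes from more cycles, and calls this conservative. That is a separate mechanism. Under-detection pulls the other way, and the net direction is unknown.
- **Prior data.** 125 mg on the 3-weeks-on schedule is the monotherapy maximum tolerated dose, with 433 subjects treated. The one monotherapy DLT at 125 mg (1 of 8) was hyperphosphatemia lasting more than 14 days, not a brief event. This tempers the likely size. It does not replace observation of the combination, which is the trial's purpose.

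A reader might infer that laboratory DLTs at 125 mg would generally go unseen, or that Table 2's Grade 3–4 rates (hypophosphatemia 7.6%, hyponatremia 6.9%, hyperphosphatemia 6.7%, lipase 6.2%) show how many. The documents support neither. Those rates are for any time on treatment and regardless of relationship, and they are not DLT rates. A calculated rise in the chance of passing 125 mg would likewise rest entirely on assumed DLT and miss rates.

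**Conclusion.** The gap is real and should be closed. For escalated subjects, all four panels have no Day 15 draw in the 125 mg DLT window, against two for a subject starting at a dose, and the only scheduled value after 125 mg exposure comes after the off week. Confidence in this reading of the calendar is high.

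The consequence is narrower. Asymptomatic abnormalities that reverse in the off week can be missed: clearly phosphorus, and possibly calcium, creatinine and others whose recovery time is not stated. Missed events favor declaring 125 mg safe. The number missed cannot be computed from the documents.

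The conclusion assumes nominal dosing and visits, and no unscheduled tests. It does not extend to symptomatic DLTs or to subjects who start at 125 mg, who have the full Cycle 1 and 2 schedule. If 1 DLT among three escalated subjects leads to three more being treated as starters at 125 mg, the six are pooled although they were observed on different schedules.

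**What to change.** Add one footnote to the safety-lab rows of Section 9:

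*For a subject whose infigratinib dose is increased to 125 mg at Cycle 3, safety labs in Cycles 3 and 4 follow the Cycle 1 and Cycle 2 schedule.*

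This adds metabolic panel and calcium/magnesium/phosphorus on C3D4 (± 1 day), and all four panels on C3D15 and C4D15 (± 3 days). Day 15 draws in the window rise from 0 to 2 for every panel, and the early chemistry and phosphorus draw is restored, matching starters.

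The cost is three lab-only draws per escalated subject. Six subjects are treated at 100 mg only after a DLT there, so at most 5 can escalate: 5 × 3 = 15 draws before replacements, or 9 if three escalate. The footnote covers escalation only and does not apply after dose reductions. Dose levels, DLT definitions, the 3+3 rule and sample size are unchanged.
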